1.1. Schedule of Activities

Table 1-1 Schedule of Activities for Study MVT-601-035

PERIOD	TREATMENT PERIOD								SAFETY FOLLOW- UP					
VISIT NAME (Timing is relative to MVT-601-3001/3002)	Week 52/Baseline (Week 52 of OLE Study; Baseline of Study)	Wk 52, Day 1	Wks 56, 60	Wk 64	Wks 68, 72	Wk 76	Wks 80, 84	Wk 88	Wk 92	Wk 96	Wk 100	Wk 104 (or Early Termination of Study Drug) ^a	Unsche duled ^b	Follow-up (~30 days after last dose of study drug) c
Visit Window (days)	OLE Study Day 365 + 10		± 7	± 7	± 7	± 7	± 7	± 7	± 7	± 7	± 7	+ 10	-	- 3 to + 18
Informed Consent	X d													
Review Eligibility Criteria	X													
Concomitant Medications ^e	X ^f		X	X	X	X	X	X	X	X	X	X	X	X
Vital Signs (BP, HR, Temperature)	X f					X						X	X g	X
Weight	X f					X						X	X g	X
Complete Physical Exam	X f											X		
Gynecologic Exam	X											X		
Signs and Symptoms- Directed Physical Exam ^h			X	X	X	X	X	X	X	X	X		X g	X
12-Lead ECG ⁱ	X f												X g	
Clinical Laboratory Tests ^j	X f			X		X						X	X g	X
Urinalysis	X f					X						X	X g	
Pregnancy Test (Urine)	X f		X	X	X	X	X	X	X	X	X	X	X g	X
Estradiol levels	X		X^{k}											
FSH ¹						X								

PERIOD	TREATMENT PERIOD								SAFETY FOLLOW- UP					
VISIT NAME (Timing is relative to MVT-601-3001/3002)	Week 52/Baseline (Week 52 of OLE Study; Baseline of Study)	Wk 52, Day 1	Wks 56, 60	Wk 64	Wks 68, 72	Wk 76	Wks 80, 84	Wk 88	Wk 92	Wk 96	Wk 100	Wk 104 (or Early Termination of Study Drug) ^a	Unsche duled ^b	Follow-up (~30 days after last dose of study drug) c
Visit Window (days)	OLE Study Day 365 + 10		± 7	± 7	± 7	± 7	± 7	± 7	± 7	± 7	± 7	+ 10	-	- 3 to + 18
Transvaginal Ultrasound ^m	X f												X g	
Bone Densitometry ⁿ	X f											X o p	X g	
Dispense Treatment q	X		X	X	X	X	X	X	X	X	X	X	X g	
Take Study Drug Dose in Clinic ^r			X	X	X	X	X	X	X	X	X	X	X g	
Daily Self- Administration of Study Drugs	X s X								X g					
Daily Completion of Paper Bleeding Diary ^t						X							X g	
Dispense Feminine Products	X		X	X	X	X	X	X	X	X	X	X	X g	
Feminine Product Collection and Venous Blood Sample ^u	X f		X	X	X	X	X	X	X	X	X	X	X g	
Treatment Compliance	X f		X	X	X	X	X	X	X	X	X	X	X g	
SF-36 Questionnaire	X		X	X	X	X	X	X	X	X	X	X		
PGA for function and symptoms Questionnaire	X		X	X	X	X	X	X	X	X	X	X		
WPAI-UF Questionnaire	X		X	X	X	X	X	X	X	X	X	X		
UFS-QoL Questionnaire	X			X		X		X			X	X		
Adverse Event Collection	X f	X	X	X	X	X	X	X	X	X	X	X	X	X
Status of Menstruation Recovery														X

Effective: 13-August-2018

Clinical Study Protocol: MVT-601-035 Effective: 13-August-2018

Abbreviations: BP, blood pressure; ECG, electrocardiogram; HR, heart rate; PGA, Patient Global Assessment; SF-36, Short Form (36) Health Questionnaire; UFS-QoL, Uterine Fibroid Symptom and Health-Related Quality of Life; WPAI-UF, Work Productivity Activity Index-Uterine Fibroid

The Week 104 visit should occur on or after the 2-year anniversary of Study Day 1 of the Parent study.

- ^c The Safety Follow-up visit may be waived if the patient enrolls directly into another relugolix clinical study upon completion of the Week 104 visit.
- d May be signed up to 30 days prior to the Week 52/Baseline visit or during the Week 52/Baseline visit. Enrollment in MVT-601-035 is defined by administration of the first dose of MVT-601-035 study drug.
- e Record all prescription and nonprescription drug and supplements taken from the Week 52/Baseline visit through the Safety Follow-up period.
- This is an MVT-601-3003 (OLE study) Week 52 procedure that serves as the Week 52/Baseline procedure for MVT-601-035 and is covered under the informed consent for the OLE study.
- The indicated procedure may be performed at the unscheduled visit based on the purpose of the visit (e.g., follow-up for an adverse event or abnormal laboratory test).
- h The exam may include a gynecologic examination, if indicated based on signs and symptoms.
- The 12-lead ECG will be submitted for central reading at the Week 52/Baseline visit. Any subsequent ECGs performed at investigator discretion will be read locally.
- Clinical laboratory tests required include clinical chemistries and a complete blood count. At the Week 52/Baseline visit and Week 104 visit, additional tests include: fasting (at least 8 hours) glucose, lipid profile, and hemoglobin A1c.
- k Pre-dose specimen drawn at Week 56 only.
- 1 Specimen for FSH will be collected on patients who have been amenorrhoeic (i.e., those who have not required the use of any feminine products) since randomization.
- Transvaginal ultrasound, with or without transabdominal ultrasound, and with or without saline or gel contrast, is performed to determine uterine and myoma volumes and to exclude any other uterine or pelvic pathology. To avoid inter-observer and inter-device variations, a single operator will be assigned to a patient and will perform each of the ultrasound scans using the same device as far as possible. Once the transvaginal ultrasound is done, a transabdominal ultrasound may also be done if the uterus cannot be adequately imaged on transvaginal ultrasound; for example, due to enlarged size. Results must be submitted to a central reader.
- ⁿ Bone densitometry (L1-L4, total hip, femoral neck) will be submitted for central reading.
- This procedure is not required at the Early Termination visit in patients whose last dose of study drug was taken during Week 60 or earlier. However, the procedure may be done if it will aid in the evaluation of an ongoing adverse event.
- Patients with a bone mineral density loss of > 7% at their Week 104/Early Termination visit relative to Parent study Baseline measurement will undergo a follow-up bone densitometry scan at 6 (± 1) months and will be contacted to question them about medications and conditions (estradiol, pregnancy) that might affect bone mineral density through the time of follow-up bone densitometry. The follow-up bone densitometry will be submitted for central reading.
- Patients will be dispensed randomized treatment at the Week 52/Baseline visit, for self-administration beginning the following day, Week 52, Day 1. Randomized treatment will be dispensed at subsequent visits until HMB (MBL ≥ 80 mL) is documented by alkaline hematin testing. When HMB has been documented, the patient will be invited for a visit to begin retreatment with open-label study drug. The timing of that visit should be within 7 days of the onset of the patient's next menses (Cycle day 1-7 where Cycle day 1 is the first day of menstrual bleeding).
- Patients will take the first dose of study drugs for this study once daily starting at Week 52, Day 1 (self-administered with phone follow-up). The last dose of study drug will be taken in the clinic during the Week 104/Early Termination visit.
- s Site to call patient and confirm first dose of study drug was taken that day.
- Patients enter diary information on menstruation status and feminine product use.
- Patients will collect and return all stained and soiled feminine products to the site with the initiation of randomized study drug treatment until return of heavy menstrual bleeding (MBL ≥ 80 mL) is observed. Collection will resume following the initiation of retreatment with open-label relugolix with add back and continue until MBL is observed to be < 80 mL on two consecutive collections. When the feminine products are returned, a venous blood sample (for hemoglobin) is to be collected and sent with the products to the central laboratory conducting the alkaline hematin assessment.

Myovant Sciences GmbH 19 CONFIDENTIAL

b Unscheduled visits may be conducted at the investigator's discretion when needed. The reason for the visit will be captured in the source documents.

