6.3. Early Termination Visit and Safety Follow-up Visit

All patients withdrawing from the study prior to Week 104 will complete an Early Termination visit. The Early Termination visit procedures are identical to those of Week 104; however, for patients whose last dose of study drug is during Week 56, bone densitometry does not need to be

performed. However, densitometry may be performed at the investigator's discretion as an aid to adverse event follow-up.

Patients who experience a return of heavy menstrual bleeding (or terminates early because they have a return of heavy menstrual bleeding) but decline retreatment with open-label study drug will complete an Early Termination visit and a 30-day Safety Follow-up visit.

Patients (including those who complete the Week 104 visit and those who withdraw early from this study) will have a follow-up visit approximately 30 days after the last dose of study drug, or prior to the date of initiation of another investigational agent or hormonal therapy affecting the hypothalamic-pituitary-gonadal axis or surgical intervention or other invasive procedure for uterine fibroids, whichever occurs first. However, the Safety Follow-up visit may be waived for patients who enroll directly into another relugolix clinical study upon completion of the Week 104 visit.

The Safety Follow-up visit will be used to assess safety after discontinuation of study treatment including adverse events, clinical safety laboratories, and return of menstruation. Refer to the Schedule of Activities (Table 1-1) for individual study visit procedures during the Safety Followup visit.

6.4. **Unscheduled Visits**

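### The schedule calls for a study-drug dose at the Early Termination visit, with no exception for women whose drug has already been stopped

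*Protocol*

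**What the plan says.** All references are to Protocol Amendment 1 (effective 13 August 2018).

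- **Table 1-1, column.** Week 104 and Early Termination share one column, headed "Wk 104 (or Early Termination of Study Drug", with the bracket then closed. The row "Take Study Drug Dose in Clinic" has a plain mark there.
- **Table 1-1, dosing footnote.** "The last dose of study drug will be taken in the clinic during the Week 104/Early Termination visit". No condition is attached.
- **Section 6.3.** "All patients withdrawing from the study prior to Week 104 will complete an Early Termination visit". It continues: "The Early Termination visit procedures are identical to those of Week 104". The one exemption it then gives is for bone densitometry after a very early last dose.
- **Section 7.8.** If a patient becomes pregnant, the site must stop study treatment at once and bring her back for an Early Termination visit. Section 4.5 likewise requires immediate withdrawal.
- **Sections 4.5 and 7.5.2.** Section 4.5 requires immediate discontinuation at listed liver-test thresholds, and Section 7.5.2 requires permanent discontinuation in potential Hy's law cases. Section 4.5 sends anyone removed from therapy to the Early Termination assessments and points to the Week 104 visit in the schedule.

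**The concern.** A site preparing an Early Termination visit works from the Schedule of Activities. Read literally, the schedule tells the site to give a dose at that visit to every woman who attends it. Some women attend precisely because the protocol has already required their drug to stop. For a pregnant woman, or one with suspected drug-induced liver injury, the schedule then states the opposite of the safety rule. What is at stake is the correctness of a drug-administration instruction in a safety setting. No efficacy or safety estimate depends on it.

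**Working it through.** No arithmetic applies. The check is whether the mark really sits in that column, and then whether the rules can be followed together.

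1. **Is the mark in the shared column?** The dose row of Table 1-1 was matched cell by cell to the header: 15 cells against 15 headers. The Week 104/Early Termination cell holds a plain mark. The densitometry row, matched in the same way, has a mark with two footnote letters in that column. The dose mark is therefore not a shifted-column artefact, and an exception was footnoted in that column for densitometry but not for the dose.

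2. **Does the text confirm the table?** Yes, twice. The dosing footnote names Early Termination expressly, and Section 6.3 equates the procedures of the two visits. The written exemptions cover one procedure, densitometry, and do not reach dosing.

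3. **Pregnancy.** Section 7.8 fixes the order: stop the drug, then attend Early Termination. Table 1-1, its footnote and Section 6.3 then place a dose at that visit. Both instructions cannot be carried out. This is a direct contradiction.

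4. **Permanent discontinuation for liver injury.** Sections 4.5 and 7.5.2 end treatment. Section 4.5 brings the woman to the Early Termination assessments, and Section 6.3 makes the procedures of that visit those of Week 104, dose included. The conflict exists but needs Section 6.3 to complete it.

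5. **Temporary withholding for liver tests.** Section 4.5 allows removal only until the cause is found and resolved, and Section 7.5.1 allows rechallenge in defined circumstances. A woman who is to resume drug need not attend Early Termination, so this group is left out.

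6. **Size.** There is one direct route (pregnancy) and one conditional route (permanent liver discontinuation). The documents give no rate for either event, so no number of affected women can be stated.

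**The case against.** The strongest reply is that specific rules govern general ones. Sections 4.5, 7.5.2 and 7.8 are mandatory and specific, and the risk table in Section 7.10 repeats immediate withdrawal for pregnancy. A woman already discontinued has no study treatment left to take, so the footnote naturally describes women still on drug. This largely stands as a prediction of what sites would do, and it is why the risk is low. It does not remove the contradiction, because no sentence says that the stop rules override the schedule.

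Second, Section 4.5 speaks of Early Termination assessments, and a dose is not an assessment. That is fair, and it weakens the liver route if Section 4.5 is read alone. Section 6.3 speaks of procedures, however, and the footnote names the dose itself.

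Third, the documents elsewhere accept that the last dose can come before the visit: the densitometry footnote concerns women "whose last dose of study drug was taken during Week 60 or earlier". This shows that the drafters knew of the case. The dosing footnote still does not provide for it.

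A reader might also infer that the table deliberately made drug marks conditional at Unscheduled visits and left them unconditional here. The documents do not support that contrast. The Unscheduled condition ("The indicated procedure may be performed at the unscheduled visit based on the purpose of the visit") is attached to nearly every mark in its column, including vital signs, laboratory tests and ultrasound. It says nothing particular about dosing.

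**Conclusion.** The point holds and is minor. The current text calls for a dose at Early Termination without exception. That directly contradicts Sections 4.5 and 7.8 for pregnancy and, through Section 6.3, conflicts with permanent discontinuation for liver injury. The stop rules would probably prevail in practice, and no endpoint or analysis changes.

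Two stronger readings are not supported. A reader might infer that the "Dispense Treatment" mark in this column is simply an error for women who complete the study, since they take their last dose at Week 104. The documents do not say whether that in-clinic dose comes from returned or newly dispensed drug, so the mark may cover its supply. SAP Section 4.3.1 allows the last randomized dose on the Week 104 visit date, which fits that reading. A reader might also infer that women who had been stopped would in fact be dosed. Nothing in the documents shows this.

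One assumption remains. The column heading carries a footnote letter whose label is lost in the available text. The sentence standing in its place concerns the two-year timing of the Week 104 visit, and the conclusion assumes that this footnote holds no dosing exception.

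**What to change.** Reword the dosing footnote along these lines: *The last dose is taken in clinic at Week 104, or at Early Termination only if the patient is still on study drug and no stop or withhold criterion is met; otherwise no study drug is taken or dispensed at that visit.* Add the same exception to the sentence in Section 6.3 that equates the two visits. The wording covers every stop rule in Section 4.5 without listing them, and it leaves the dispensing mark in place for women who complete Week 104.

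The cost is one reworded footnote and one added clause. No procedure is added, every other Early Termination assessment stays as it is, and the SAP needs no change.

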2. INTRODUCTION

2.1. Uterine Fibroids with Heavy Menstrual Bleeding

Uterine leiomyomas (often referred to as fibroids or myomas) are common benign, estrogendependent tumors that grow in the muscular wall of the uterus and occur in approximately 75% of women by the onset of menopause. While the majority of uterine fibroids are asymptomatic, approximately 25% of women with fibroids develop symptoms requiring treatment [Stewart, 2001; Stewart, 2017]. The most problematic symptom for women with uterine fibroids is heavy menstrual bleeding, with menstrual periods of increased duration and volume. In women with uterine fibroids, menstrual periods can last as long as 10 to 14 days rather than the usual 5 to 7 days, and blood loss can be as high as 300 to 500 mL, with anything more than 80 mL during a given cycle considered abnormal. The heavy menstrual bleeding associated with uterine fibroids is likely caused by the increase in surface area of the uterine cavity, poor uterine contraction due to the myoma, and increased circulation, congestion, or impaired hemostasis due to hypertrophy of the endometrium near the myoma [Hapangama, 2016]. Persistent heavy menstrual bleeding can induce iron-deficiency anemia and associated fatigue and loss of energy. Heavy menstrual bleeding is a primary reason for the deterioration in the health-related quality of life assessed in patients with uterine fibroids and is a major cause of elective hysterectomy. Other symptoms include bulk symptoms, such as pain or pressure in the abdomen and pelvis due to large myoma(s), low back pain, urinary frequency or urinary tract obstruction, constipation, and pregnancy loss.

The incidence of uterine fibroids increases as women grow older, and risk factors include nulliparity, obesity, family history, black race, and hypertension. Fibroids typically arise during the reproductive years, tend to enlarge during pregnancy, and regress after menopause as these tumors are dependent upon estrogen and progesterone for their growth. Transvaginal ultrasound is used most commonly to diagnose these benign tumors, and magnetic resonance imaging, sonohysterography, and hysteroscopy are used to evaluate their size and position. The type of treatment recommended for uterine fibroids typically depends upon their size, location, the patient's age, reproductive plans, and obstetrical history. Few medical options are available for women with heavy menstrual bleeding associated with uterine fibroids, and approximately 60% of women who received medical therapy in one study underwent a surgical procedure within 2 years [Marjoribanks, 2006], suggesting many women are inadequately treated with the currently available medical therapies.

Gonadotropin-releasing hormone (GnRH) agonists such as leuprolide acetate (also known as leuprorelin) are effective in lowering estrogen and progesterone levels, decreasing menstrual bleeding, and decreasing fibroid size. However, they cannot be used for more than 6 months due to bone mineral density loss from the resulting hypoestrogenic state. The GnRH agonists, which are administered by injection at 1- or 3-month intervals, first stimulate secretion of luteinizing hormone (LH) and follicle-stimulating hormone (FSH), which, in turn, increase estradiol and progesterone levels resulting in a flare of clinical symptoms. This initial rise in hormonal levels is followed by a gradual decline in levels over 4 weeks as the pituitary becomes desensitized to the chronic stimulation of the GnRH agonist and LH and FSH levels fall. Other medical treatments are used but have limited clinical effectiveness, including tranexamic acid, aromatase inhibitors, nonsteroidal anti-inflammatory medications, and danazol.

Effective: 13-August-2018

The current mainstay of treatment for women with heavy menstrual bleeding associated with uterine fibroids is surgery. Several surgical procedures are frequently performed including myomectomy by various techniques, endometrial ablation, endometrial uterine artery embolization, and magnetic resonance-guided focused-ultrasound surgery. Each of these procedures has complications. For example, abdominal myomectomy results in complications requiring hysterectomy in up to 3 to 4% of cases, along with the frequent development of intraoperative adhesions [Gliklich, 2011]. Furthermore, recurrence of heavy menstrual bleeding after myomectomy is common, with at least 25% of women requiring additional treatment [Stewart, 2015; Marret, 2012; ACOG Practice Bulletin No. 96, 2008]. Hysterectomy is the definitive procedure with more than 200,000 hysterectomies performed annually in the United States (US) for uterine fibroids [Farquhar, 2002; Wu, 2007]. Major complications have been reported to occur in up to 25% of women undergoing hysterectomy, including infection, severe bleeding, and injuries to the urethra, bowel, or bladder. One study showed that among women with Medicaid insurance who underwent abdominal hysterectomy, there was a 10% risk of transfusion and up to a 28% risk of medical or surgical complications including major blood loss, wound infection, and febrile episodes [Gliklich, 2011].

Approximately 3 million women in the US suffer from symptomatic uterine fibroids that are inadequately treated with medical therapy, and related US health care costs for uterine fibroids exceeds \$34 billion [Stewart, 2015; Cardozo, 2012; Gliklich, 2011]. There is a great need for a safe and efficacious medicine that can decrease the symptoms of uterine fibroids so women have an alternative to myomectomy and hysterectomy.

2.2. Relugolix

The current relugolix Investigator's Brochure summarizes the nonclinical toxicology and previous human experience with relugolix. The previous human experience with relugolix includes results of phase 1 and phase 2 studies evaluating relugolix monotherapy in women with uterine fibroids or endometriosis and in men with prostate cancer, and phase 3 studies in women with uterine fibroids. The Investigator's Brochure also provides a full discussion of the safety profile of relugolix.

2.2.1. Indication

Relugolix 40 mg with estradiol 1.0 mg/norethindrone acetate 0.5 mg (relugolix with E2/NETA) is being developed as a once-daily oral medication for the treatment of heavy menstrual bleeding associated with uterine fibroids. The proposed dose of relugolix is 40 mg administered orally once daily, and the proposed doses of estradiol and norethindrone acetate are 1.0 mg and 0.5 mg once daily, respectively.

2.2.2. **Pharmacology**

Relugolix is an orally-active, potent, highly selective high-affinity small-molecule GnRH receptor antagonist with a novel structure. Relugolix was discovered and initially studied by Takeda Pharmaceutical Company Limited, before development rights outside of Japan and certain East Asian countries were licensed to Myovant Sciences GmbH.

Effective: 13-August-2018

Relugolix antagonizes human GnRH receptors present on gonadotropin-secreting cells of the anterior pituitary by competitively inhibiting binding of the active ligand, GnRH, to the GnRH receptors. In the absence of GnRH-stimulated secretion by the anterior pituitary, levels of LH and FSH fall rapidly, followed by a decline over a few days in estradiol and progesterone levels. Relugolix acts as a potent and highly selective antagonist for the human GnRH receptor. The affinity of relugolix for the human GnRH receptor in vitro was approximately 50-fold higher than that of GnRH in the presence of protein (40% fetal bovine serum). Transgenic knock-in mice expressing the human GnRH receptor when treated with relugolix had substantial reductions in reproductive organ weights of both female and male mice, suggesting that relugolix may suppress blood estrogen and testosterone levels, respectively. Orally administered relugolix suppressed the hypothalamic-pituitary axis in castrated cynomolgus monkeys at doses of 1 mg/kg and higher.

